8.2.5 Follow-up of Participants after Adverse Events

8.2.5.1 *Investigator Follow-up*

Treatment of any adverse events will be determined by the Investigator using his/her best medical judgment and according to current clinical practice guidelines. All applied measures as well as follow-up will be recorded in the appropriate eCRF.

The Investigator will continue follow-up on adverse events, including laboratory abnormalities and solicited adverse events, until the event has resolved, is otherwise satisfactorily explained, or the participant completes the study. The resolution date will be recorded on the eCRF as the last date on which the participant experienced the adverse event. If an adverse event resolution date is uncertain the Investigator should estimate the completion date based on medical judgment and interview of the participant. Approximate dates of resolution from phone or other communications may be taken as adverse event resolution dates. Some examples of estimation of adverse event resolution are: 1) an asymptomatic laboratory abnormality on one visit that has not been followed-up between visits but has resolved by the next visit may be assumed to have resolved by the midpoint of the inter-visit interval; 2) A resolved adverse event that was treated may be assumed to have been resolved by the end of treatment.

Adverse events that are still present at the end of the study should be recorded as ongoing.

Information recorded on the eCRF must be substantiated in the source documents. If an adverse event evolves into a condition that becomes “serious,” it will be designated as serious on the adverse event eCRF and a supplemental SAE report form will be completed.

Follow-up for SAEs must continue until resolution and the outcome reported to the Sponsor, even if this extends beyond the SAE reporting period.

8.2.6 Post-study Adverse Events

At the final study visit, the Investigator should instruct each participant to report to the Investigator any subsequent adverse events that the participant's personal physician believes could be related to study vaccine or study procedures.

The Investigator should notify the Sponsor (or designee) of any death, SAE or other adverse event of concern occurring at any time after a participant has discontinued study vaccine if the event is believed to be related to study vaccine or study procedures. The Sponsor (or designee) should also be notified if the Investigator becomes aware of the development of cancer or a congenital anomaly/birth defect in a subsequently conceived offspring of a participant that participated in this study.

The Investigator should record the event in the eCRF; if the eCRF is no longer available, the Investigator should report the event directly to the Sponsor (or designee).

8.3 Other Events of Special Interest

Adverse events of special interest represent a subset of adverse events that include autoimmune diseases and other systemic disorders of interest which could potentially have an autoimmune aetiology. The Investigator should use clinical and scientific judgment in deciding whether other adverse events (i.e. events not listed here) could have an autoimmune origin and should therefore be reported as AESIs (see [Section 8.2.4](#)).

8.4 Overdoses or Incorrect Administration

Study vaccine overdose is the accidental or intentional use of the study vaccine in an amount higher than the dose being studied. An overdose or incorrect administration of study vaccine is not an adverse event unless it results in untoward medical effects:

- Any study vaccine overdose or incorrect administration of study vaccine should be recorded in the eCRF as part of the study vaccine administration information
- Any untoward medical effects associated with an overdose or incorrect administration of study vaccine should be recorded in the eCRF as an adverse event.

If the associated adverse event fulfils serious criteria, the event should be reported to the Sponsor (or designee) within 24 hours of knowledge of the event

8.5 Management of Pregnancy

8.5.1 Notification and Follow-up

Any pregnancies occurring during the study or within 6 months after the last dose of study vaccine must be reported to the Sponsor (or designee) within 24 hours of knowledge of the event. The paper pregnancy form should be completed with all information known at the time and scanned and emailed to [REDACTED]

Female participants of childbearing potential will be instructed to immediately inform the Investigator if they become pregnant during the reporting window and must be immediately discontinued from study vaccine. The Investigator should counsel the participant, discussing

the risks of the pregnancy and the unknown effects on the foetus. Monitoring of the participant should continue until conclusion of the pregnancy.

Male participants will be instructed to immediately inform the Investigator if their partner becomes pregnant during the reporting window. Attempts should be made to collect and report details of the course and outcome of any pregnancy in the partner of a male participant exposed to study vaccine. The pregnant partner will need to sign an authorisation for use and disclosure of pregnancy health information to allow for follow-up on her pregnancy. The Investigator may provide information on the risks of the pregnancy and the unknown effects on the foetus, to support an informed decision in cooperation with the treating physician and/or obstetrician.

8.5.2 *Outcome*

Additional information on the course and outcome of the pregnancy should be provided to the Sponsor (or designee) when available using the pregnancy report form.

The following pregnancy outcomes will be considered to be SAEs and should be reported according to the procedure in [Section 8.2.4](#). Pregnancy is not considered an adverse event unless one of these criteria is met:

- Spontaneous abortion (as the Sponsor considers spontaneous abortions to be medically significant events)
- Any congenital anomaly/birth defect in a child born to a female participant or female partner of a male participant

9 DATA QUALITY ASSURANCE AND QUALITY CONTROL

9.1 Protocol Violations and Deviations

Major protocol deviations are defined as those that result in harm to the study participants or significantly affect the scientific value of the reported results of the study. Other deviations will be considered minor.

Protocol deviations will be recorded on the source documents and with an explanation for the deviation. All protocol deviations will also be recorded as specified in the monitoring plan and statistical analysis plan (SAP).

Major protocol deviations that meet the criteria for a serious breach of ICH GCP [34] should be reported to the Sponsor immediately. No deviation from the inclusion/exclusion criteria will be permitted.

9.2 Monitoring and Source Document Verification

The Sponsor will arrange for the study to be monitored in accordance with the principles of ICH GCP [34]. The frequency of monitoring visits will be determined by the rate of participant recruitment.

The following are examples of items that will be reviewed at these visits:

- Compliance with the protocol
- Consent procedure
- Source documents
- Adverse event procedures
- Storage and accountability of study vaccine

The monitoring visits also provide the Sponsor with the opportunity to ensure that timely participant accrual and the other Investigator's obligations and all applicable requirements are being fulfilled.

The Investigator must permit the Study Monitor, the HRA/REC, the Sponsor's auditors and representatives from Competent Authorities direct access to all source documents (see [Section 11.1](#)) for confirmation of the accuracy and reliability of data contained within the eCRF (source document verification). Participant confidentiality will be protected at all times. The Study Monitor will carry out source document verification at regular intervals. This is an essential element of quality control, as it allows the rectification of transcription errors and omissions.

9.3 Data Management and Coding

Data for each participant will be recorded on an eCRF. Data collection must be completed for each participant who signs an informed consent form and receives at least one dose of study vaccine.

Electronic CRFs will be designed and produced by the Sponsor (or designee) and should be completed in accordance with instructions. The Investigator is responsible for maintaining adequate and accurate medical records from which accurate information will be transcribed directly into the eCRFs using a secure internet connection. The eCRFs should be filled out completely by the Investigator (or designee) as stated on the delegation of responsibilities form.

The eCRF system will be Food and Drug Administration (FDA) Code of Federal Regulations (CFR) 21 Part 11 compliant.

The eCRFs must be reviewed and approved by the Investigator.

Data entered into the eCRF will be validated as defined in the data validation specifications. Validation includes, but is not limited to, validity checks (e.g. range checks), consistency checks and customised checks (logical checks between variables to ensure that study data are accurately reported) for eCRF data and external data (e.g. laboratory data). A majority of edit checks will be triggered during data entry and will therefore facilitate efficient 'point of entry' data cleaning.

Data management personnel will perform both manual eCRF review and review of electronic edit checks to ensure that the data are complete, consistent and reasonable. The electronic edit checks will run continually throughout the course of the study and the issues will be reviewed manually online to determine what action needs to be taken.

Manual queries may be added to the system by clinical data management, local Medical Monitor or Study Monitor. Clinical Data Managers and Study Monitors are able to remotely and proactively monitor the eCRFs to improve data quality.

External data will be transferred electronically into the study database. Discrepancies will be queried to the study centre and/or the laboratory until the electronic data and the database are reconciled.

All updates to queried data will be made by authorised study team members only and all modifications to the database will be recorded in an audit trail. Once all the queries have been resolved, eCRFs will be locked. Any changes to locked eCRFs will be approved by the Investigator.

Once the full set of eCRFs has been completed and locked, and SAE reconciliation has been completed, the Sponsor will authorise database lock and all electronic data will be sent to the designated statistician for analysis. Subsequent changes to the database will then only be made only by written agreement of the Sponsor. The Investigator will be provided with a copy of the eCRFs in a non-editable format.

Adverse events and medical/cancer history terms will be coded from the verbatim description (Investigator term) using the Medical Dictionary for Regulatory Activities (MedDRA) (Version 22.0 or later). Prior and concomitant medications and therapies will be coded according to the World Health Organisation drug dictionary (Version Drug B3 Global September 2019). Coding review will be performed by the Sponsor (or designee) prior to database lock.

The clinical data (in SAS[®] dataset format) will be transferred to the Sponsor at the end of the study.

10 STATISTICAL CONSIDERATIONS AND ANALYSIS PLAN

10.1 Sample Size Determination

No formal sample size calculation for cohorts 1 to 4 was performed and sample size is based upon feasibility considerations. The chosen number of participants is considered sufficient to meet the objectives for the study.

The sample size for cohorts 5 and 6 is based on the ELISpot results of ChAdOx1-HBV administered to healthy adults at a dose of 2.5×10^{10} which resulted in a mean of 1,000 +/-500 spot forming units in three adults who had samples examined by same day analysis at Oxford University. Assuming the same response in 15 volunteers in each cohort, the sample size is powered to detect a 45% decrease in the T cell response in the participants receiving prior AZD1222 compared to the Pfizer/Moderna mRNA COVID-19 vaccine.

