4 STUDY POPULATION

4.1 Number of Participants

It is planned that 40 healthy participants and 12 participants with CHB infection and virally suppressed with oral antiviral medication will be enrolled in the study. Chronic HBV participants will be recruited/deemed eligible by hepatologists, infectious disease specialists or physicians experienced in treating CHB participants. Centres not meeting the enrolment expectations will be considered for replacement with or addition of a new site. If participants leave the study before all follow-up visits are completed (for any reason), then these may be replaced at the discretion of the study team. A log of all participants enrolled into the study (i.e. having given informed consent) will be maintained in the Investigator's Site File (ISF) at the study centre irrespective of whether they have treated with vaccine or not.

A total of 10 healthy participants and 12 participants with CHB infection is considered sufficient to confirm the safety, tolerability and immunogenicity of ChAdOx1-HBV and to answer the objectives of the study before progressing to larger studies. An additional 30 healthy participants (15 who have received two doses of AZD1222 and 15 who have received at least two doses of either Pfizer or Moderna mRNA COVID-19 vaccine) will be recruited to assess whether prior receipt of AZD1222 results in decreased T cell responses to ChAdOx1-HBV.

The statistical considerations used to determine the number of participants planned and evaluable are presented in [Section 10.1](#).

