5.7 Method of Assigning Participants to Treatment Groups

At the screening visit, participants will be sequentially allocated a participant number once written, informed consent has been obtained. They will be identified by this number throughout the study.

In cohorts 1-4, the healthy and CHB participants will be allocated to low dose or high dose treatment depending on the treatment schedule prepared by statistician.

As cohorts 5 and 6 were introduced following completion of enrolment of the healthy participants in cohorts 1 and 2, all further healthy participants enrolled under protocol version 7.0 and 8.0 will receive high dose treatment.

Participants fulfilling entry criteria will be allocated to treatment based on a treatment schedule.

Once participant numbers have been assigned, no attempt will be made to use those numbers again. If a participant number is allocated incorrectly, no attempt will be made to remedy the error once the study vaccine has been dispensed. Any participants that are withdrawn prior to vaccination will be replaced on a case by case basis following discussion with the Sponsor. Discontinued participants following vaccination who do not complete all follow-up visits will be replaced at the determination of the Sponsor.

Any replacement participants will be given the next sequential participant number.

The treatment schedule list will be held by the statistician during the study.

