8. SAMPLE SIZE

The number of participants is based on feasibility considerations rather than formal sample size calculations. A total of 10 healthy participants and 12 participants with CHB infection is considered sufficient to confirm the safety, tolerability and immunogenicity of ChAdOx1-HBV and to answer the objectives of the study before progressing to larger studies.

The sample size for cohorts 5 and 6 is based on the ELISpot results of ChAdOx1-HBV administered to healthy adults at a dose of 2.5×10^{10} which resulted in a mean of 1,000 +/-500 spot forming units in three adults who had samples examined by same day analysis at Oxford University. Assuming the same response in 15 volunteers in each cohort, the sample size is powered to detect a 45% decrease in the T cell response in the participants receiving prior AZD1222 compared to the Pfizer/Moderna mRNA COVID-19 vaccine.

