10.1.3. Statistical Testing and Estimation

No formal statistical analysis is planned.

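### Cohorts 5 and 6 are called powered for a 45% decrease, but the SAP plans no cohort 5 versus cohort 6 estimate, confidence interval or named visit

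*Protocol*

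**What the plan says.** **Sample size.** Protocol 10.1 and SAP 8 use the same justification. Earlier ELISpot data at the high dose gave a "mean of 1,000 +/-500 spot forming units in three adults". Then, "Assuming the same response in 15 volunteers in each cohort", both documents state that "the sample size is powered to detect a 45% decrease in the T cell response" in those with prior AZD1222 relative to those with prior mRNA vaccine. Neither document gives an alpha, a sidedness, a power level, a test or a scale, or says whether ±500 is an SD or a standard error.

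**Purpose.** Protocol 4.1 says the 30 added participants are recruited "to assess whether prior receipt of AZD1222 results in decreased T cell responses to ChAdOx1-HBV". SAP 5.2 lists this as a secondary objective for cohorts 5 and 6, and SAP 6 (like the Protocol synopsis) says the T cell responses of the two groups are to be compared.

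**Analysis.** SAP 10.1.3 reads "No formal statistical analysis is planned", and SAP 10.1.7 relies on this to set multiplicity aside. For ELISpot, SAP 10.7.2 and Table 14.2.4 give n, mean, SD, median and range of the background-subtracted response and its change from baseline, by treatment group, antigen combination and visit. The SAP 10.7.2 paragraph on previous ChAdOx1 exposure adds listings only. SAP 11 does not record the missing comparison as a change from the Protocol.

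**The concern.** A power statement describes how a particular analysis behaves. Here the sample size section claims power for a between-cohort decrease, and the analysis sections contain no between-cohort quantity that the claim could refer to.

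Cohorts 5 and 6 exist to answer one practical question. Protocol 1.5.1 says they are meant to support the three-month interval after AZD1222, and concedes that the interval does not rest on firm data. Two columns of group means leave the reader to judge by eye. Similar means could be taken as evidence of no interference although the data are still compatible with a large loss. Equally, a chance gap in one antigen combination at one visit could be taken as interference. SAP 10.7.2 names four antigen combinations, and cohorts 5 and 6 have three post-vaccination immunology visits (Days 14, 28 and 84). That makes 4 × 3 = 12 side-by-side comparisons of absolute response, none of them designated as the answer.

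**Working it through.** **Inputs**
- Reference mean 1,000 SFU and spread ±500 from three adults (Protocol 10.1, SAP 8). Reading ±500 as an SD is an assumption.
- n = 15 per cohort. No dropout allowance is stated, but Protocol 5.7 says "Discontinued participants following vaccination who do not complete all follow-up visits will be replaced at the determination of the Sponsor".
- Effect: 45% of 1,000 = 450 SFU.
- Alpha, sidedness, power and test are not stated. The values below are assumptions, varied to show their effect.

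**1. Can the 45% be reproduced?** With SD 500 in both cohorts, the standard error of the difference is 500 × √(2/15) = 182.6 SFU, and 450/182.6 = 2.465.
- One-sided 5%, normal approximation: power = Φ(2.465 − 1.645) = Φ(0.820) = 79.4%. The decrease detectable with 80% power is (1.645 + 0.842) × 182.6 = 454 SFU, or 45.4%.

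So one-sided 5% with about 80% power returns the stated figure.

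**2. How far does the answer move with what is unstated?** Power for a 45% decrease, 15 per cohort:

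| Reading | Power |
|---|---|
| Two-sided 5% t-test, SD 500 in both cohorts (noncentral t, 28 df, ncp 2.465) | 66% |
| One-sided 5%, SD 500 in both: t-test / normal approximation | 78% / 79% |
| Two-sided 5% Welch test, SD proportional to mean (500 and 275) | 83% |
| Two-sided 5% t-test, log scale, CV 50% | 92% |

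- Welch row: SE = √((500² + 275²)/15) = 147.3, and 450/147.3 = 3.05 on 21.8 df.
- Log row: σ = √ln(1 + 0.5²) = 0.472; −ln(0.55) = 0.598; 0.598/0.472 = 1.27 SD. It takes no account of values set to zero.
- If ±500 is a standard error, the SD is 500 × √3 = 866 and the two-sided equal-SD t-test has 28% power.

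**3. How firm is the SD?** With three adults (2 df) and normal data, the 95% interval for the SD runs from 500 × √(2/7.378) = 260 to 500 × √(2/0.0506) = 3,142.

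**4. What would an interval tell the reader?** On the log scale with 15 per cohort, the 95% limits are the observed ratio multiplied and divided by exp(2.048 × σ × √(2/15)). The CV is an assumption, shown over a range:
- CV 50%: σ = 0.472, factor exp(0.353) = 1.42. An observed ratio of 1.00 would give 0.70 to 1.42, excluding a decrease of more than about 30%.
- CV 100%: σ = 0.833, factor exp(0.623) = 1.86. An observed ratio of 1.00 would give 0.54 to 1.86, excluding only decreases of more than about 46%.

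The planned tables do not report which of these situations the trial is in.

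**The case against.** The strongest reply has three parts.

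First, this is a small, open-label, non-randomised phase 1 study, and Protocol 10.2.2.1 says most of the analysis will be descriptive. That is a fair reason not to require a hypothesis test. It is no reason to omit an estimate with an interval, which is itself descriptive and is what the objective asks for.

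Second, Table 14.2.4 reports n, mean and SD by group, so a reader could form a raw-scale interval. This works for a single antigen combination. For the total response it does not, because the SD of a sum cannot be recovered from the SDs of its parts; the reader would have to rebuild totals from Listing 16.2.6.3. The visit would also still be chosen after seeing the data. The further analyses that the SAP places elsewhere do not fill the gap: SAP 10.7.2 mentions them for intracellular cytokine staining, and the AZD1222 item in SAP 10.7.3 concerns flow cytometry, not ELISpot.

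Third, the objective is directional, and one-sided 5% returns 45%. This stands. A reader might infer from the 66% row that the sample size is miscalculated, or from the matching two-sided 5% equal-SD result (80% power needs a 53% decrease) that the cohorts are underpowered. The documents do not support either inference. Two-sided 5%, an 80% target and a common SD are not stated in them, and other readings they permit give 79%, 83% or 92%.

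**Conclusion.** The concern holds as a mismatch between the sample size claim and the analysis. The Protocol and SAP call 15 per cohort powered for a between-cohort decrease and make that question a secondary objective. The SAP then specifies no cohort 5 versus cohort 6 contrast, no interval and no visit. As written, the plan cannot say how large a decrease the data exclude. This does not depend on what alpha or sidedness was intended.

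The 45% figure is unverifiable as stated, not wrong. The 66% to 92% range is a set of sensitivity values under named assumptions with ±500 read as an SD, and it shows why the inputs need writing down. All of the values rest on variability seen in three adults.

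It would also go too far to say that a true 45% loss would be missed about one time in three. That applies only to a two-sided equal-SD t-test, and no test is planned. Finally, the cohorts are not randomised and their eligible intervals since COVID-19 vaccination differ (10 to 18 weeks against 6 to 30), so a confidence interval would express sampling error only.

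**What to change.** 1. In SAP 10.1.3 and 10.7.2, make an exception for this comparison. Report the cohort 5 / cohort 6 geometric mean ratio of total ELISpot response with its 95% CI, at one visit named before database lock. Other visits and single antigen combinations become supportive.
2. Define total response, including which of the four combinations are summed. State the offset for values set to 0. SAP 10.1.1 defaults to adding 1, whereas SAP 10.7.2 sets ELISpot results that do not exceed 25 to zero, so zeros may pull strongly on a log-scale mean. The choice should be deliberate.
3. Restate the power sentence in Protocol 10.1 and SAP 8 with alpha, sidedness, power level, test, scale and the meaning of ±500, calculated for the analysis in item 1. A raw-scale figure should not be printed beside a log-scale analysis. Give the result over a range of CVs, since the source is three adults.
4. Add the ratio and its interval to Table 14.2.4 or a companion table, and adjust SAP 10.1.7, which says no statistical analysis is planned.

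The cost is one added estimate from ELISpot data already in the schedule and wording in two documents. It needs no more participants, samples or visits.
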